2.1.3 Rapamycin vs. ABI-009 (nab-Rapamycin)

Rapamycin (sirolimus) is a potent allosteric inhibitor of mTORC1; yet, it has low oral bioavailability, poor solubility, and dose-limiting intestinal toxicity.^{1,21} Temsirolimus, a prodrug of rapamycin and the only current intravenous "rapalog" preparation, has low water-solubility requiring formulation in surfactants and solvents; when infused, temsirolimus can potentially cause hypersensitivity reactions and decreased drug efficacy.²¹ ABI-009, nab-Rapamycin, is a novel human albumin-bound intravenous preparation of rapamycin. Albumin nanoparticle technology encapsulates lipophilic drugs into nanoparticles by combining drug and human serum albumin in a water based solvent under high pressure, resulting in nanoparticle size in the range of 100-200 nM.²² This technology enhances permeability and retention (EPR) allowing accumulation of macromolecules (*i.e.* drug albumin nanoparticles) in solid tumors.

This increased permeability and retention is important due to the underlying pathophysiology of tumor tissue defined by angiogenesis, defective lymphatic drainage, and abnormal vascular architecture.²² ABI-009 is formulated in saline, has low anaphylaxis potential, and may improve drug delivery and efficacy.²¹

Proof of this concept has been demonstrated in preclinical studies comparing albumin-bound paclitaxel nanoparticles (nab- paclitaxel or ABI-007) vs. paclitaxel. Improved drug accumulation and antitumor response, as well as, enhanced biodistribution and increase in the maximum tolerated dose (MTD) was observed in the ABI-007 treated mice compared to those treated with paclitaxel.²² Adult phase 1, 2 and 3 clinical studies of ABI-007 showed no hypersensitivity reactions when compared to paclitaxel; ABI-007 showed increased response rates (33% vs. 19%) and prolonged tumor progression (22 vs. 16.9 weeks) in patients with metastatic breast cancer.²²

2.1.4 Rationale for Combination Therapy and Starting Dose

There have been numerous clinical trials evaluating mTOR inhibition in combination with a variety of chemotherapy backbone regimens in both adult and pediatric trials. Specifically, COG has investigated mTOR inhibition in combination with cyclophosphamide and vinorelbine (ARST0921) and in combination with irinotecan (IRN) and temozolomide (TMZ) (ADVL0918).^{23,24} Of the combinations noted above, IRN and TMZ is of most interest due to its activity in heavily pretreated patients. The COG study ANBL0421, evaluated this backbone in patients with recurrent or refractory neuroblastoma. In this cohort, eight of the first 50 evaluable patients had objective responses to treatment.²⁵ In addition to evaluating this combination in neuroblastoma, other studies have investigated this backbone in relapsed Ewing sarcoma, rhabdomyosarcoma, and other difficult to treat solid tumors suggesting its feasibility in children.

These studies contributed to the development of a COG Phase 1 trial (ADVL0918) evaluating temsirolimus (TEM) in combination with IRN and TMZ. This was a dose finding study evaluating escalating doses of intravenous TEM, oral TMZ, and oral IRN. Seventy-one eligible patients were enrolled with a variety of solid tumor diagnoses, including CNS. Dose limiting toxicities included elevated serum alanine aminotransferase and triglycerides, anorexia, and thrombocytopenia. The MTD was identified as TEM 35 mg/m² weekly on Days 1, 8, and 15 with IRN 90 mg/m² and TMZ 125 mg/m² on Days 1-5 of a 21-day cycle. Of the seventy-one patients enrolled, six patients had objective responses with three of those having sustained responses for ≥ 14 cycles of therapy.²³

To further delineate a starting dose of ABI-009, a review of published adult PKs of temsirolimus²⁶ and ABI-009²¹ noted a starting dose of 45 mg/m². When administered temsirolimus produces the sirolimus metabolite, and the AUC of temsirolimus + sirolimus metabolite from temsirolimus at a dose of 45 mg/m² is 3414 + 11740 = 15,154 ng•h/ml. Since the molecular weight of temsirolimus (1030 g/mol) is similar to the molecular weight of sirolimus (914 g/mol), AUCs were summed without adjustment. The AUC of sirolimus from ABI-009 at 45 mg/m² is 24,564 (ng•h/ml) which is at least twice the total exposure compared to temsirolimus based on sirolimus alone. Thus the AUC of sirolimus from ABI-009 is substantially higher than that from temsirolimus at an equal dose (45 mg/m²) of both drugs. A similar higher exposure of sirolimus with ABI-009 compared to temsirolimus would be expected at the lower dose

of 35 mg/m². Given that in the ADVL0918 study, the dose of 35 mg/m² of temsirolimus was well tolerated in combination, the starting dose for ABI-009 was extrapolated to start at 35 mg/m², understanding that this would roughly double the exposure of temsirolimus.

Furthermore, the phase 1 trial evaluating ABI-009, determined that the majority of missed doses (83%) occurred on day 15 (the 3rd dose of every 4-week schedule) (data unpublished). As a result, AADi has recently started two new phase 2 studies that incorporate the 2-dose, 3-week schedule. Based upon this information, the starting dose for this pediatric trial will mimic ADVL0918 on a Day 1 and Day 8 schedule. This will allow for rapid translation of the results of this trial into disease specific studies within COG.

2.2 Preclinical Studies

The activity of the combination of chemotherapy and mTOR inhibition was studied in preclinical models.

2.2.1 Antitumor Activity

Biochemical and functional characterization of ABI-009 has been undertaken in preclinical studies. These studies have suggested exceptional drug efficacy and safety, as well as decreased cancer cell viability and downstream signaling in several xenograft cancer models, including pancreatic, colorectal, breast cancer, and multiple myeloma.²⁷⁻³⁰ Significant antitumor activity was observed across all tumor models tested at 40 mg/kg.²⁸

Increased antitumor activity was noted when ABI-009 was used in combination with either ABI-007, doxorubicin, SAHA, erlotinib or perifosine.²⁷⁻³⁰

2.2.2 Animal Toxicology

One study evaluated overall toxicity of ABI-009 in breast and colon xenograft models at dose levels of 0, 15, 30, 45, 90 and 180 mg/kg on an every 4 days times 3 schedule; pharmacokinetic properties were evaluated at dose levels of 1, 15, 30, and 45 mg/kg, and antitumor activity was evaluated at 40 mg/kg with a 3 times weekly for 4 weeks schedule. The investigators noted that ABI-009 was non-toxic at the dose level of 180 mg/kg; no changes were noted in blood chemistry, CBC, hypercholesterolemia, or hypertriglyceridemia. ABI-009 showed no CNS side effects in xenograft models tested.²⁷⁻³⁰

2.2.3 Preclinical Pharmacokinetic Studies

With respect to dose, ABI-009 exhibited linear Pharmacokinetics.²⁸

2.3 Adult Studies

2.3.1 Phase 1 Studies

The first in-human trial of ABI-009 administered at 5 dose levels (45, 56.25, 100, 125, and 150 mg/m²) on a weekly schedule for 3 weeks followed by 1 week of rest in patients with advanced solid tumors. The maximum tolerated dose (MTD) was 100 mg/m² with the most common toxicities including thrombocytopenia (58%), hypokalemia (23%), mucositis (38%), fatigue (27%), rash (23%), diarrhea (23%),

nausea (19%), anemia (19%), hypophosphatemia (19%), neutropenia (15%), and hypertriglyceridemia (15%). The study initially dose escalated from 100 mg/m² to 150 mg/m² which resulted in 4 dose-limiting toxicities (DLTs), two at 150 mg/m² and two at 125 mg/m²; these were grade 3 AST elevation and grade 4 thrombocytopenia and grade 3 suicidal ideation and grade 3 hypophosphatemia, respectively (CTCAE v.4). The MTD had only 1 grade 3 non-hematologic event (dyspnea) and 1 grade 3 hematologic event (anemia) after cycle 1 (CTCAE v4). Twenty-seven patients were enrolled on this trial; however, only 19 were evaluable for efficacy. There was 1 patient with adenocarcinoma of the kidney with a partial response, two patients with stable disease (mesothelioma and neuroendocrine tumor) with prolonged stabilization for 1 year and 238 days, respectively.²¹

2.3.2 Phase 2 Studies

No Phase 2 studies have been conducted to date.

2.3.3 Pharmacology/Pharmacokinetics/Correlative and Biological Studies

The pharmacokinetic analysis showed an almost proportional increase of the maximum concentration (C_{max}) and area under the curve (AUC) with the outlier being a moderately low AUC at 125 mg/m². The C_{max} of ABI-009 was 3227.61 ng/mL that is significantly higher than levels achieved in other studies evaluating oral rapamycin and intravenous temsirolimus.^{31,32} The half-life was 40–91 hours across the tested dose range and was 63 hours at the MTD of 100 mg/m². Circulating levels of the biomarkers S6K1 and 4EBP1 were significantly inhibited by ABI-009 and inhibition was maintained for several days after administration at dose levels greater than 56.25 mg/m².

2.4 **Pediatric Studies**

No pediatric studies of ABI-009 have been conducted. The Pediatric Preclinical Testing Program (PPTP) evaluated rapamycin in their xenograft models and noted a broad antitumor activity, with a significant activity in sarcoma models.³³ The Children's Oncology Group (COG) evaluated, in a Phase 2 trial (ARST0921), bevacizumab and temsirolimus in combination with vinorelbine (V) and cyclophosphamide (C) for initial relapse/progression for patients with RMS. Patients were randomized between the bevacizumab plus VC arm vs. temsirolimus plus VC arm. Patients that were randomized to the temsirolimus arm had a significantly improved EFS compared to the bevacizumab arm, 65% vs. 50%, respectively.²⁴ In addition, there have been multiple Phase 1 and 2 trials evaluating mTOR inhibitors including oral rapamycin, everolimus and temsirolimus alone or in combination in pediatric patients.¹³

2.4.1 Prior Experience in Children

There have been no pediatric studies of ABI-009.

2.5 **Overview of Proposed Pediatric Study**

We propose to conduct a Phase 1 study of ABI-009 in children with relapsed/refractory solid tumors using the rolling 6 design. Cycle 1 will aim to establish tolerability and safety and to

obtain pharmacokinetics of ABI-009 as a single agent dosed on days 1 and 8 of a 21-day cycle. Additionally, Cycle 2+ will aim to determine the MTD and/or RP2D of ABI-009 in combination with temozolomide and irinotecan. The ABI-009 starting dose will be 35 mg/m² as a single agent during Cycle 1, while Cycle 2+ dosing and scheduling in combination with irinotecan (90 mg/m²) and temozolomide (125 mg/m²) will mimic the Phase 1 pediatric trial ADVL0918.²³

2.6 Rationale for Amendment #4 (Addition of Dose Level -2 and modification of the definition of hematological DLT)

With Amendment #4, an additional Dose Level -2 of 15 mg/m² has been added. To date (08/21/19), 18 patients have enrolled onto the study. Five patients enrolled at Dose Level 1 (35 mg/m²); two of these patients experienced a DLT of platelet count decrease within the first one to three cycles of protocol therapy. An additional 13 patients enrolled at Dose Level -1 (20 mg/m²) of which 7 patients are inevaluable. There were 2 DLTs (platelet count decrease) observed among the 6 evaluable patients. This amendment will provide a dose reduction to 15 mg/m² (Dose Level -2). We have reviewed our PK data for both Dose Level 1 (35 mg/m²) and Dose Level -1 (20 mg/m²). The data notes the median AUC for Dose Level 1 and Dose Level -1 to be 11,561 (ng•h/mL) and 8,599 (ng•h/mL), respectively. These median AUCs at these dose levels are well above the published AUCs for both temsirolimus and sirolimus. A Pediatric phase 1 trial evaluated weekly temsirolimus in refractory/recurrent solid tumors at doses of 10, 25, 75, and 150 mg/m² on days 1, 8, and 15.³⁴ The reported PK data indicates a median AUC for temsirolimus at doses of 10, 25, 75, and 150 mg/m² to be 1670, 3570, 2810, and 5190 (ng•h/mL), respectively.³⁴ In addition, sirolimus PK data was also investigated in this trial as following administration temsirolimus produces the sirolimus metabolite.³⁴ The median AUCs for sirolimus in this study at the above doses were 2560, 4520, 7670, and 8660 (ng•h/mL), respectively.³⁴ Review of the nab-rapamycin pharmacokinetics in adults demonstrates high variability (% coefficient of variation (CV), up to 40%) in both C_{max} and AUC.²¹ In addition, for children and adolescent who received nab-rapamycin on this trial, PK parameters also had significantly variability (CV at least 35%). At Dose Level -1 (20mg/m²): C_{max} (mean 374 µg/L, median 368 µg/L, CV 39%); AUC_{inf} (mean 10113 µg•h/L, median 9749 µg•h/L, CV 37%); Clearance (mean 2.2 L/h/m², median 2 L/h/m², CV 35%). As noted previously, initial dosing for this study mimic the MTD in ADVL0918.²³ This study evaluated temsirolimus at 15mg/m² in combination with irinotecan and temozolomide, thus further validating this suggested dose reduction.²³ In addition, Raymond et al, noted in their trial evaluating the safety and efficacy of CCI-779, a novel mTor inhibitor, a partial response in a patient with renal cell carcinoma at a dose of 15 mg/m². Thus, based upon the information, above, a dose reduction of ABI-009 to 15 mg/m² is likely to yield a higher AUC then noted in the previous pediatric phase 1 trial of temsirolimus and that this dose would be in the therapeutic range. Given the significant variability in exposures as dose reduction to 15 mg/m² (Dose Level -2) ensures an adequate margin of safety with potential for clinical benefit.

Due to the fact that all of the DLTs experienced thus far in this study have been hematologic DLTs, no patients with known bone marrow involvement will be enrolled (Stratum 2). Therefore, all enrolled participants will be evaluable for hematological toxicity. DL-2 will be evaluated with modified definitions of hematological DLT. Based on experience to date and the DLT evaluation period including both cycle 1 and cycle 2, we have increased the accrual ceiling to include a 30% rate of patients who are not evaluable for toxicity, rather than 20%.

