11.1.1 Amendment #4

The projected maximum number of additional (i.e., in addition to the 18 already enrolled) evaluable patients required to complete the study with this amendment is 12. This includes 6 evaluable patients at DL -2 and 6 additional evaluable patients in a PK expansion cohort. Therefore, the projected maximum number of additional patients enrolled into the study allowing for 30% inevaluability is 18, and this number is expected to be accrued over 9-18 months. The overall study will have an expected maximum of 36 patients.

The study design includes several contingencies that may increase the maximum sample size if all contingencies are needed to estimate the MTD. A maximum of 26 additional patients may be possible in the unlikely scenario that DL-2 requires expansion to 12 patients plus 6 additional patients for pharmacokinetic analysis and a 30% inevaluable rate. The maximum sample size of 26 additional patients could accrue over an additional 13-26 months. The overall study will have an absolute maximum enrollment of 44 patients.

11.2 **Definitions**

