11.2.2 Maximum Tolerated Dose

- The MTD will be the maximum dose at which fewer than one-third of patients experience a DLT (See [Section 5.5](#)) during Cycles 1 and 2 of therapy.
- In the unlikely event that two DLTs observed out of 6 evaluable patients are different classes of Adverse Effects (e.g. hepatotoxicity and myelosuppression), AND all of the following conditions are met, expansion of the cohort to 12 patients will be considered:
 - One of the DLTs does not appear to be dose-related
 - The Adverse Effects are readily reversible
 - The study chair, DVL statistician, DVL committee chair or vice chair, and IND sponsor all agree that expansion of the cohort is acceptable

If fewer than 1/3 of patients in the expanded cohort experience dose-limiting toxicities, the dose escalation can proceed.

- The DLTs observed in the pharmacokinetic (PK) expansion cohort will be counted towards the total number of DLTs observed at the MTD during the dose escalation portion of the study. If $\geq 1/3$ of the cohort of patients at the MTD (during the dose escalation plus the PK expansion) experience DLT then the MTD will be exceeded.

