11.3.1 Amendment #4

Patients will be enrolled at DL -2 using the rolling 6 study design. If DL -2 is determined to be safe (at most 1 out of 6 evaluable patients with DLT), then up to 6 more patients will be enrolled at DL -2 in a PK expansion cohort. If DL -2 is determined to not be tolerable (2 or more dose limited patients out of 6 evaluable patients), the study will be closed to accrual.

11.4 **Inclusion of Children, Women and Minorities**

The study is open to all participants regardless of gender or ethnicity. Review of accrual to past COG studies of new agents demonstrates the accrual of both genders and all NIH-identified ethnicities to such studies. Efforts will be made to extend the accrual to a representative population, but in a Phase 1 trial which will accrue a limited number of patients, a balance must be struck between patient safety considerations and limitations on the number of individuals exposed to potentially toxic or ineffective treatments on the one hand and the need to explore gender, racial, and ethnic aspects of clinical research on the other. If differences in outcome that correlate to gender, racial, or ethnic identity are noted, accrual may be expanded or additional studies may be performed to investigate those differences more fully.

The gender and minority distribution of the study population is projected to be¹:

Racial Categories	Ethnic Categories				Total
	Not Hispanic or Latino		Hispanic or Latino		
	Female	Male	Female	Male	
American Indian/ Alaska Native	0	0	0	0	0
Asian	1	1	0	0	2
Native Hawaiian or Other Pacific Islander	0	0	0	0	0
Black or African American	2	4	0	0	6
White	9	14	4	1	28
More Than One Race	0	0	0	0	0
Total	12	19	4	1	36

PHS 398 / PHS 2590 (Rev. 08/12 Approved Through 8/31/2015) OMB No. 0925-0001/0002

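### Is the 30% inevaluable allowance in Amendment #4 too low, given 7 of 13 inevaluable at Dose Level -1?

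*Combined protocol and SAP*

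**What the plan says.** Section 2.6 reports the position when Amendment #4 was written: "To date (08/21/19), 18 patients have enrolled onto the study". Five of these were at Dose Level 1, with no inevaluable count given. For the rest: "An additional 13 patients enrolled at Dose Level -1 (20 mg/m²) of which 7 patients are inevaluable", and "There were 2 DLTs (platelet count decrease) observed among the 6 evaluable patients". Later in the section patients with known marrow involvement are excluded, with the stated result that everyone enrolled can be assessed for hematological toxicity. Modified hematological DLT definitions are also announced for Dose Level -2. The allowance comes next: "we have increased the accrual ceiling to include a 30% rate of patients who are not evaluable for toxicity, rather than 20" percent.

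Section 11.1.1 applies the 30%. For 12 further evaluable patients (6 at Dose Level -2 and 6 in the PK expansion), the projected maximum of "additional patients enrolled into the study allowing for 30% inevaluability is 18, and this number is expected to be accrued over 9-18 months". If Dose Level -2 had to expand to 12 patients, a case the section calls unlikely, the target is 18 evaluable and the figure is 26 additional patients. It concludes: "The overall study will have an absolute maximum enrollment of 44 patients".

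Two other provisions bear on the consequences. Section 11.3.1 says that if Dose Level -2 is safe, "then up to 6 more patients will be enrolled at DL -2 in a PK expansion cohort". Section 11.2.2 says: "The DLTs observed in the pharmacokinetic (PK) expansion cohort will be counted towards the total number of DLTs observed at the MTD".

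**The concern.** The allowance is said to rest partly on experience, yet the experience reported is worse than 30%. The other stated reason, the two-cycle window, does not by itself explain a rate below the one observed, because a longer window gives more chances to become inevaluable. The ceilings also have almost no slack: they meet their targets on average only if the inevaluable rate stays at or below about 33% (18 patients) or 31% (26 patients).

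If the true rate were nearer 39%, the plan could reach its ceiling with the PK expansion or the 12-patient contingency unfilled. Because DLTs in the expansion count in the final MTD check, a shortfall would also reduce the denominator of that check. The overall totals of 36 and 44, the projected enrollment table in Section 11.4 and the accrual durations all rest on the same 30%.

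**Working it through.** **Inputs.** 18 enrolled, 5 at Dose Level 1 and 13 at Dose Level -1, with 7 of the 13 inevaluable (Section 2.6). Evaluable targets of 12 and 18, and a 30% allowance (Section 11.1.1). MTD exceeded if one-third or more have a DLT (Section 11.2.2).

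**1. The plan's own figures.** Enrollment needed = evaluable target / (1 - inevaluable rate).
- 12 / 0.70 = 17.1, rounded up to 18; 18 + 18 = 36 overall.
- 18 / 0.70 = 25.7, rounded up to 26; 18 + 26 = 44 overall.

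All four stated figures reproduce.

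**2. Observed rates.** At Dose Level -1, 7/13 = 53.8%. Overall, 7/18 = 38.9% if all five Dose Level 1 patients were evaluable, so this is a floor. Two of those five had a DLT, so at most three could be inevaluable, giving an upper limit of 10/18 = 55.6%.

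**3. Do the counts contradict 30%?** Exact 95% intervals are 17% to 64% for 7/18 and 25% to 81% for 7/13. At a true rate of 30%, the chance of 7 or more inevaluable is 0.28 among 18 and 0.06 among 13. The data lean above 30% without excluding it.

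**4. Margin.** Break-even rates are (18 - 12)/18 = 33.3% and (26 - 18)/26 = 30.8%.

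**5. Yield if a higher rate persisted.** Expected evaluable = enrolled × (1 - rate); chances are binomial.

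| Inevaluable rate | Yield from 18 | P(at least 12) | Yield from 26 | P(at least 18) | P(at least 6 of 18) | P(at least 12 of 26) |
|---|---|---|---|---|---|---|
| 30% | 12.6 | 0.72 | 18.2 | 0.63 | 0.9997 | 0.997 |
| 38.9% | 11.0 | 0.41 | 15.9 | 0.26 | 0.996 | 0.96 |
| 53.8% | 8.3 | 0.07 | 12.0 | 0.015 | 0.91 | 0.58 |

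The last column assumes that replacements may run up to the 26-patient ceiling.

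**6. Effect on the one-third rule.** Smallest DLT count that reaches one-third:
- n = 12: 4 (4/12 = 33.3%; 3/12 = 25.0%). n = 11: 4 (4/11 = 36.4%; 3/11 = 27.3%).
- n = 18: 6 (6/18 = 33.3%; 5/18 = 27.8%). n = 16: 6 (6/16 = 37.5%; 5/16 = 31.3%).

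The trigger is the same at the target and at the 39% yield. At the 54% yields it falls: 3 of 8 (37.5%) in place of 4 of 12, and 4 of 12 in place of 6 of 18. The fraction applied is still one-third, with less precision.

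**7. What a higher rate would require.** At 38.9%: 12 / (11/18) = 19.6, so 20; 18 / (11/18) = 29.5, so 30; 38 and 48 overall. At 53.8%: 12 / (6/13) = 26 and 18 / (6/13) = 39; 44 and 57 overall.

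**The case for a change.** The strongest case for a change is that every rate consistent with the reported counts, from 39% to 56%, lies above 30%, although the section says experience informed the figure. At 39% the chance of reaching the evaluable target drops from 0.72 to 0.41 in the projected case and from 0.63 to 0.26 in the maximum case. A sentence giving the reason for 30%, or a recalculated ceiling, would cost little.

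The numbers stand. The inference that the plan must change does not, for four reasons.

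- **The old rate may not carry over.** Section 2.6 places the marrow exclusion and the revised DLT definitions directly before the 30% figure, and the dose is lower. Section 11.2.1 ties evaluability to receiving at least 85% of the prescribed dose in each of two cycles, so tolerability can affect it. The available text does not say why the seven were inevaluable, so a lower rate can be neither shown nor ruled out. Part of Section 2.6 was missing from the text examined, so no claim can be made that an explanation is absent.
- **A shortfall breaks no rule.** The expansion has an upper limit and no minimum, and 12 is a projected maximum. Sections 11.2.1 and 11.3 replace inevaluable patients. ABI-009 sampling starts in Cycle 1 (Section 8.3.2.1), so a patient who becomes inevaluable for DLT in Cycle 2 can still supply single-agent PK data.
- **The larger gap sits in an unlikely branch.** The 26-patient case needs two DLTs of different classes among six (Section 11.2.2). Section 2.6 says all DLTs so far were hematological, and Section 11.3.1 otherwise closes accrual at two of six.
- **A higher ceiling has a price.** Moving from 44 to 48 enlarges a pediatric phase 1 trial on the strength of a rate from 18 patients treated under different conditions. In the projected case the difference is only two patients, 20 against 18.

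**Conclusion.** No change is needed. The totals 18, 26, 36 and 44 follow exactly from the stated 30%, and that figure is a defensible planning input: 7 of 18 does not exclude it, and the conditions at Dose Level -2 differ from those in which the counts arose. If 39% did persist, the expected cost is about one evaluable patient in the projected case (11.0 against 12) and about two in the maximum case (15.9 against 18). The DLT count that triggers the one-third rule would be the same, and the six-patient decision at Dose Level -2 would be almost certain to be reached (0.996).

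This rests on treating patients' evaluability as independent with a common rate, and on 39% as the working alternative although it is a floor. At 54% the expansion would probably fall short, with about 8 evaluable of the 12 intended, but the six-patient decision would still have a 0.91 chance of being reached within 18 patients. The margin above 30% is thin. Stating the expected yield at 39% would help a reader, but it would alter no rule or analysis.
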